4.2.3 Concomitant therapy

All medications (excluding prior chemotherapy and biologic, immunologic or radiation therapy) taken within 4 weeks prior to the administration of buparlisib/sonidegib and all concomitant therapy administration during the study with reasons for therapy should be recorded. All prior chemotherapy; biologic, immunologic or radiation therapy; and surgery within 4 weeks prior to the administration of study drug, will be recorded.

Patients on chronic medications that can be given concomitantly with buparlisib/ sonidegib should be maintained on the same dose and dose schedule throughout the study period, as medically feasible. The investigator should instruct the patient to notify the study site about any new medications he/she takes after the start of the study drug. All medications (other than study drug) and significant non-drug therapies (including herbal medicines, physical therapy and blood transfusions) administered after the patient starts treatment with study drug, and any changes in dosing should be recorded.

In general, the use of any concomitant medication/therapies deemed necessary for the care of the patient is permitted with the following exceptions described below in Section

4.2.3.1 Drugs that are prohibited

- ♦♦ Other investigational therapies must not be used while the patient is on the study.
- ◆◆ Anticancer therapy (chemotherapy, biologic or radiation therapy, and surgery) other than the study treatments must not be given to patients while the patient is on the study. If such agents are required for a patient then the patient must be discontinued from the study.
- ♦ In vitro metabolism studies suggest that oxidative metabolism of buparlisib is predominantly mediated by CYP3A4 (fm>0.9), with only minor contributions of CYP1A1. As buparlisib is a sensitive CYP3A4 substrate, co-administration of buparlisib with strong and moderate CYP3A4 inhibitors and CYP3A4 inducers is prohibited. Refer to Table 15 for a list of prohibited drugs. Please note this list may not be comprehensive.
- Based on in vitro studies, co-administration of buparlisib with CYP3A4 inducers is predicted to decrease the systemic exposure to buparlisib, thereby increasing the risk of exposing the patient to subtherapeutic drug levels. Refer to Table 15 for a list of prohibited CYP3A inducers. Please note that this list may not be comprehensive. Therapeutic doses of warfarin sodium (Coumadin®) or any other coumadin-derivative anticoagulants are not permitted.
- •• If a patient requires the concomitant use of any medication included in Table 16 entitled "List of Prohibited QT prolonging drugs" (ie, drugs that are generally accepted by the Qtdrugs.org Advisory Board of the Arizona CERT to have a risk of causing Torsades des de Pointes), study treatment administration must be interrupted as long as the patient requires therapy with the QT prolonging agent.
- ♦♦ Herbal preparations/medications are not allowed throughout the study. These herbal medications include, but are not limited to St. John's wort, Kava, ephedra (ma huang), ginko biloba, dehydroepiandrosterone (DHEA), yohimbe, saw palmetto, ginsing. Patients should stop using these herbal medications 7 days prior to first dose of study drug.

◆◆ Hormonal contraceptives may be affected by cytochrome P450 interactions, and are therefore not considered effective in this study.

Table 15. List of prohibited CYP3A Inhibitors and Inducers

СҮРЗА	Inhibitors	СҮРЗ	3A Inducers
Strong	Moderate	Strong	Moderate
clarithromycin conivaptan grapefruit juice Indinavir itraconazole ketoconazole Lopinavir Mibefradil nefazodone Nelfinavir posaconazole Ritonavir Saquinavir	aprepitant atazanavir cimetidine ciprofloxacin darunavir diltiazem erythromycin fluconazole tofisopam verapamil amprenavir fosamprenavir elvitegravir tipranavir	avasimibe carbamazepine Phenobarbital (barbiturate) phenytoin rifabutin rifampin St John's Wort	bosentan efavirenz etravirine modafenil nafcillin ritonavir talviraline tipranavir
telithromycin troleandomycin voriconazole			

This database of CYP inhibitors was compiled from the Indiana University School of Medicine's "Clinically Relevant" Table and from the University of Washington's Drug Interaction Database based on *in vitro* studies. Strong inhibitors are predicted to increase buparlisib AUC > 5-fold, and moderate inhibitors are predicted to increase buparlisib AUC ≥ 2-fold but < 5-fold.

This database of CYP inducers was compiled from the FDA's "Guidance for Industry, Drug Interaction Studies;" from the Indiana University School of Medicine's "Clinically Relevant" Table; and from (Pursche *et al.* 2008).

All QT-prolonging drugs listed in Table 4-8 are prohibited for all patients from screening through permanent discontinuation of study treatment. Table 16 below lists drugs with a known risk for Torsades de Pointes (TdP) as well as sensitive CYP3A substrates (with narrow TI) with a possible or conditional risk for TdP.

Table 16. List of prohibited QT-prolonging drugs

Drug	QT risk(*)	Comment
Amiodarone	Known risk for TdP	Females > Males, TdP risk regarded as low
Arsenic trioxide	Known risk for TdP	
Astemizole	Known risk for TdP	No Longer available in U.S.
Bepridil	Known risk for TdP	Females>Males
Chloroquine	Known risk for TdP	
Chlorpromazine	Known risk for TdP	
Cisapride	Known risk for TdP	Restricted availability; Females > Males.
Disopyramide	Known risk for TdP	Females > Males
Dofetilide	Known risk for TdP	
Domperidone	Known risk for TdP	Not available in the U.S.
Droperidol	Known risk for TdP	
Halofantrine	Known risk for TdP	Females>Males
Haloperidol	Known risk for TdP	When given intravenously or at higher-than- recommended doses, risk of sudden death, QT prolongation and torsades increases.
Ibutilide	Known risk for TdP	Females>Males
Levomethadyl	Known risk for TdP	
Mesoridazine	Known risk for TdP	
Methadone	Known risk for TdP	Females > Males
Pentamidine	Known risk for TdP	Females > Males
Pimozide	Known risk for TdP	Females > Males
Probucol	Known risk for TdP	No longer available in U.S.
Procainamide	Known risk for TdP	
Quetiapine	Possible risk for TdP	Prohibited as this drug is a sensitive 3A4 substrate
Quinidine	Known risk for TdP	Females > Males
Sotalol	Known risk for TdP	Females > Males
Sparfloxacin	Known risk for TdP	
Tacrolimus	Possible risk for TdP	Prohibited as this drug is a sensitive 3A4 sibstrate with narrow TI

Terfenadine	Known risk for TdP	No longer available in U.S.
Thioridazine	Known risk for TdP	
Drug	QT risk(*)	Comment

^(*) Classification according to the Qtdrugs.org Advisory Board of the Arizona CERT Sensitive substrates: Drugs whose plasma AUC values have been shown to increase 5fold or higher when co-administered with a potent inhibitor of the respective enzyme.

4.2.3.2 Drugs to be used with caution

Preliminary in vitro metabolism studies suggest that buparlisib is a weak, reversible inhibitor CYP3A4/5 (Ki=13.6 μM, [I]/Ki= 0.4 where [I] is the average C_{max} at steady-state following 100 mg daily dose) and a weak reversible inhibitor of CYP2C8/2C9/2C19 (IC₅₀=34 μM, [I]/IC₅₀=0.15). Note: that with the data available, we are not able to confirm whether such interactions will occur in patients. Therefore, investigators, at their discretion, may administer concomitant medications known to be metabolized by CYP3A4/5, CYP2C8, CYP2C9 and CYP2C19. Patients receiving such medications must be carefully monitored for potentiation of toxicity due to any individual concomitant medications, and may require dose titration or reduction of the drug substrate. Please refer to Table 17 for a list of CYP450 substrates and carefully consider their co-administration with buparlisib.

Particularly, caution is advised when buparlisib is coadministered with:

- ◆◆ Drugs which are substrates for CYP3A4, CYP2C8, CYP2C9 or CYP2C19 and which have a narrow therapeutic index.
- ◆◆ Oral anti-diabetics which are metabolized by CYP2C8 or CYP2C9 can possibly result in hypoglycemia. Patients who develop diabetes mellitus during the study should be treated according to the American Diabetes Association guidance. It is recommended that treatment start with metformin.
- ♦♦ If a patient, after study enrollment, requires the concomitant use of any QT prolonging medication with a possible or conditional risk for torsade de pointes then the investigators, at their discretion, may co-administer such medications. Patients receiving such medications must be monitored. Refer to Table 16 for a list of QT-prolonging medications to be used with caution.

Note: please refer also to Table 16 for a list of prohibited QT prolonging medication.

- ◆◆ Please refer to Table 17 for a list of CYP450 substrates and carefully consider their co-administration with buparlisib.
- ♦♦ Concomitant treatment with corticosteroids and buparlisib should be avoided, whenever possible, during this study. A short duration (< 2 weeks) of systemic corticosteroids is allowed (eg, for chronic obstructive pulmonary disease, or as an anti-emetic). Chronic dosing of corticosteriods is known to induce CYP3A enzymes, thereby increasing the risk or reducing buparlisib overall exposure to sub-therapeutic levels.

Table 17. List of CYP450 Substrates to be used with caution

CYP2C8	CYP2C9	CYP2C19		CYP3A**
CYP2C8	CYP2C9	CYP2C19		CYP3A**
amodiaquine cerivastatin pioglitazone repaglinide rosiglitazone torasemide troglitazone	celecoxib diclofenac flurbiprofen fluvastatin Glibenclamide (glyburide) gliclazide glimepiride glipizide indomethacin irbesartan ketobemidone lornoxicam losartan meloxicam naproxen nateglinide piroxicam rosiglitazone S- ibuprofen sulfamethoxazo le tenoxicam tolbutamide torasemide valdecoxib	amitriptyline citalopram clobazam clomipramine clopidogrel diazepam fluoxetine imipramine lansoprazole mephobarbital moclobemide omeprazole pantoprazole progesterone quazepam rabeprazole sertraline S-mephenytoin	Adinazolam alfentanil ^{1,2} Alpha- dihydroergocryptine 1 Alprazolam Amlodipine Aripiprazole Atorvastatin Brecanavir brotizolam ¹ budesonide ¹ buspirone ¹ Capravirine Cerivastatin Chlorpheniramine cyclosporine ² darifenacin ¹ Diazepam diergotamine ² ebastine ¹ eletriptan ¹ eplerenone ¹ ergotamine ² Estazolam everolimus 1	felodipine ¹ fentanyl ² flunitrazepam fluticasone ¹ lovastatin ¹ maraviroc ¹ midazolam ¹ nifedipine nisoldipine nitrendipine perospirone ¹ quinine sildenafil ¹ simvastatin ¹ sirolimus ^{1,2} tolvaptan trazodone triazolam ¹

Table 17. List of CYP450 Substrates to be used with caution (continued)

^{*} This database of CYP substrates was compiled from the Indiana University School of Medicine's "Clinically Relevant" Table, and from (Zhou *et al.* 2009)

^{**} CYP3A substrates were compiled from the Indiana University School of Medicine's "Clinically Relevant" Table; and supplemented by the FDA's "Guidance for Industry, Drug Interaction Studies" and the University of Washington's Drug Interaction Database.

Sensitive substrates: Drugs whose plasma AUC values have been shown to increase 5-fold or higher when co-administered with a potent inhibitor of the respective enzyme.

Substrates with narrow therapeutic index (NTI): Drugs whose exposure-response indicates that increases in their exposure levels by the concomitant use of potent inhibitors may lead to serious safety concerns (eg, Torsades de Pointes).

Table 18. List of QT prolonging drugs to be used with caution

Table 18. List of QT prolonging drugs to be used with caution			
Drug	QT risk	Comment	
Alfuzosin	Possible risk for Torsades de Pointes		
Amantadine	Possible risk for Torsades de Pointes		
Amitriptyline	Conditional risk for Torsades de Pointes		
Azithromycin	Possible risk for Torsades de Pointes		
Chloral hydrate	Possible risk for Torsades de Pointes		
Citalopram	Conditional risk for Torsades de Pointes		
Clomipramine	Conditional risk for Torsades de Pointes		
Clozapine	Possible risk for Torsades de Pointes		
Desipramine	Conditional risk for Torsades de Pointes		
Diphenhydramine	Conditional risk for Torsades de Pointes		
Dolasetron	Possible risk for Torsades de Pointes		
Doxepin	Conditional risk for Torsades de Pointes		
Dronedarone	Possible risk for Torsades de Pointes		
Felbamate	Possible risk for Torsades de Pointes		
Flecainide	Possible risk for Torsades de Pointes		
Fluoxetine	Conditional risk for Torsades de Pointes		
Foscarnet	Possible risk for Torsades de Pointes		
Fosphenytoin	Possible risk for Torsades de Pointes		
Galantamine	Conditional risk for Torsades de Pointes		
Gatifloxacin	Possible risk for Torsades de Pointes		
Gemifloxacin	Possible risk for Torsades de Pointes		
Granisetron	Possible risk for Torsades de Pointes		
Imipramine	Conditional risk for Torsades de Pointes		
Indapamide	Possible risk for Torsades de Pointes		

Isradipine	Possible risk for Torsades de Pointes	
Levofloxacin	Possible risk for Torsades de Pointes	
Lithium	Possible risk for Torsades de Pointes	
Mexiletine	Conditional risk for Torsades de Pointes	
Drug	QT risk	Comment
Moexipril/HCTZ	Possible risk for Torsades de Pointes	
Moxifloxacin	Possible risk for Torsades de Pointes	
Nicardipine	Possible risk for Torsades de Pointes	
Nortriptyline	Conditional risk for Torsades de Pointes	
Drug	QT risk	Comment
Octreotide	Possible risk for Torsades de Pointes	
Ofloxacin	Possible risk for Torsades de Pointes	

	1	1	
Ondansetron	Possible risk for Torsades de Pointes		
Oxytocin	Possible risk for Torsades de Pointes		
Paliperidone	Possible risk for Torsades de Pointes		
Paroxetine	Conditional risk for Torsades de Pointes		
Perflutren lipid microspheres	Possible risk for Torsades de Pointes		
Protriptyline	Conditional risk for Torsades de Pointes		
Ranolazine	Possible risk for Torsades de Pointes		
Risperidone	Possible risk for Torsades de Pointes		
Roxithromycin*	Possible risk for Torsades de Pointes	*not available in the	
		United States	
Sertindole	Possible risk for Torsades de Pointes		
Sertraline	Conditional risk for Torsades de Pointes		
Solifenacin	Conditional risk for Torsades de Pointes		
Tizanidine	Possible risk for Torsades de Pointes		
Trazodone	Conditional risk for Torsades de Pointes		
Trimethoprim-Sulfa	Conditional risk for Torsades de Pointes		
Trimipramine	Conditional risk for Torsades de Pointes		
Venlafaxine	Possible risk for Torsades de Pointes		
Ziprasidone	Possible risk for Torsades de Pointes		
(*) Classification according to the Qtdrugs.org Advisory Board of the Arizona CERT			

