1.4.2 Muscular system

In the phase 1 trial (LDE225X2101), dose-limiting skeletal muscle toxicities characterized by CTCAE Grade 3 or Grade 4 creatinine kinase (CK) elevation associated with muscle pain and elevated plasma myoglobin have been observed in a dose and exposure dependent manner. No evidence of cardiac muscle toxicity has been observed. The majority of cases of CTC Grade 3/4 elevated CK, occurred 3 to 6 weeks after continuous daily treatment with sonidegib. Following the discontinuation of sonidegib, the majority of DLTs resolved over a period of approximately 4-8 weeks. Re-challenge with sonidegib at a lower dose appeared not to cause subsequent CK elevation. The DLTs were described in some cases as rhabdomyolysis, however, no impairment in renal function was been observed in any of the affected patients.

In the CLDE225A2112 drug-drug interaction study, one patient developed rhabdomyolysis with renal failure, which necessitated treatment with hemodialysis, as described in Section 5.2.1.8. Muscular activities such as strenuous exercise that can result in significant increases in plasma CK levels should be avoided while on sonidegib treatment. Patients who are taking statins appear to be at increased risk of developing Grade 3/4 CK elevation and therefore statins should be avoided while taking sonidegib. If it is essential that the patient stays on a statin to control hyperlipidemia, only pravastatin may be used with extra caution.

Patients should be assessed for the development of muscle symptoms such as myalgia, myopathy and/or muscle spasms. Serum creatinine and plasma levels of CK, CK-MB, and myoglobin should be closely monitored during the first 8 weeks and throughout treatment with sonidegib. If clinically significant increases in CK levels are detected, serum creatinine must be checked and the patients must be monitored for signs and symptoms of rhabdomyolysis. Management using supportive therapy including adequate hydration may be considered according to standard medical practice, institutional and applicable protocol-specific guidelines.

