3.1 Overall study design

This is an open-label, single-center 2-cohort pilot study, as shown in Figure 4. All patients will receive LB therapy until evidence of progression, intolerable toxicities or withdrawal from the study.

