- 16. Patients who have taken herbal medications and certain fruits within 7 days prior to starting study drug. Herbal medications include, but are not limited to St. John's Wort, Kava, and ephedra (ma huang), dehydroepiandrosterone (DHEA), gingko biloba, yohimbe, saw palmetto, and ginseng. Fruits include the CYP3A inhibitors Seville oranges, grapefruit, pummelos, or exotic citrus fruits.
- 17. Patients who are currently treated with drugs known to be moderate and strong inhibitors or inducers of isoenzyme CYP3A, and the treatment cannot be discontinued or switched to a different medication prior to starting study drug. Please refer to Table 15 for a list of prohibited inhibitors and inducers of CYP3A (Please note that co-treatment with weak inhibitors of CYP3A is allowed).
- 18. Patients who have received chemotherapy or targeted anticancer therapy ≤ 4 weeks (6 weeks for nitrosourea, antibodies or mitomycin-C) prior to starting study drug must recover to a Grade 1 before starting the trial
- 19. Patients who have received any continuous or intermittent small molecule therapeutics (excluding monoclonal antibodies) ≤ 5 effective half-lives prior to starting study drug or who have not recovered from side effects of such therapy
- 20. Use of statin drugs or other medications known to associate with rhabdomyolysis. These drugs must be discontinued at enrollment.

- 21. Patients who have received wide field radiotherapy ≤ 4 weeks or limited field radiation for palliation ≤ 2 weeks prior to starting study drug or who have not recovered from side effects of such therapy
- 22. Patients who have undergone major surgery ≤ 2 weeks prior to starting study drug or who have not recovered from side effects of such therapy.
- 23. Patients who are currently taking therapeutic doses of warfarin sodium or any other coumadin-derivative anticoagulant. Low molecular weight heparin is allowed.

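### The on-study prescribing rules do not carry section 1.4.2's advice to avoid statins during sonidegib, and Table 17 leaves five non-pravastatin statins to investigator discretion

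*Combined protocol and SAP*

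**What the plan says.** Section 1.4.2 (Muscular system) says that patients taking "statins appear to be at increased risk of developing Grade 3/4 CK elevation and therefore statins should be avoided while taking sonidegib". It then allows pravastatin alone, with extra caution, when a statin cannot be given up.

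The rules for prescribing during the study are in section 4.2.3, which begins from a permissive default: "In general, the use of any concomitant medication/therapies deemed necessary for the care of the patient is permitted with the following exceptions". The exceptions follow in 4.2.3.1, and no statin is among them. Section 4.2.3.2 covers drugs to be used with caution and states: "Therefore, investigators, at their discretion, may administer concomitant medications known to be metabolized by CYP3A4/5, CYP2C8, CYP2C9 and CYP2C19". It requires careful monitoring of such patients for potentiated toxicity and refers to Table 17. That table's CYP3A column includes "Aripiprazole Atorvastatin Brecanavir" and its CYP2C9 column includes "celecoxib diclofenac flurbiprofen fluvastatin Glibenclamide".

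The entry rule is exclusion 20 in section 3.2.2.2: "Use of statin drugs or other medications known to associate with rhabdomyolysis. These drugs must be discontinued at enrollment". Section 3.1 sets no fixed treatment length: "All patients will receive LB therapy until evidence of progression, intolerable toxicities or withdrawal from the study".

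**The concern.** An investigator who needs to know whether a patient on treatment may have a statin will look in section 4.2.3. There the drug appears under caution and not under prohibited. Following that section as written, the investigator could give a drug that section 1.4.2 says to avoid.

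The question can plausibly arise. Statins are withdrawn at enrollment, and section 4.3.5.2 then calls for cholesterol and triglycerides on the first day of odd-numbered cycles. Tables 9 and 10 have no lipid row. Their rows for other adverse events would cover a treatment-related lipid event, but only for study-drug dosing; they do not say which lipid-lowering drug may be used.

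What is at stake is patient safety. Section 1.4.2 describes dose-limiting muscle toxicity with sonidegib and one case, in a drug-interaction study, of rhabdomyolysis with renal failure that needed hemodialysis.

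**Working it through.** This is a comparison of texts, with a small count and one check on the CK data.

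1. **The rule.** Section 1.4.2 covers statins as a class, for as long as sonidegib is taken, with pravastatin the single exception. It sets no dose threshold.

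2. **The prohibited list.** The bullets in 4.2.3.1 deal with investigational therapy, anticancer therapy, CYP3A4 inhibitors and inducers, coumarin anticoagulants, Table 16 QT drugs and herbal products, and remark on hormonal contraceptives. None names statins or drugs linked to rhabdomyolysis. Tables 15 and 16 also contain no statin, but they list CYP3A and QT drugs, so none would be expected there. The informative fact is the missing bullet.

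3. **The caution list.** Statin entries in Table 17:
   - CYP2C8: cerivastatin (1)
   - CYP2C9: fluvastatin (1)
   - CYP2C19: none (0)
   - CYP3A: atorvastatin, cerivastatin, lovastatin, simvastatin (4)

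   Total 1 + 1 + 0 + 4 = 6 entries. Cerivastatin appears twice, so 6 − 1 = 5 distinct statins. Pravastatin is not one of them. The reason given in 4.2.3.2 is buparlisib's weak inhibition of CYP enzymes; sonidegib muscle toxicity is not mentioned.

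4. **The entry rule.** Exclusion 20 fixes a time to stop. It does not speak about starting or restarting a statin later, and treatment runs until progression, intolerable toxicity or withdrawal.

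5. **The entry documents against each other.**
   - Pravastatin: section 1.4.2 and Appendix B exclusion item 8 allow it when essential. Exclusion 20 and item 19 make no exception, and section 3.2.2.2 says a patient must meet none of the exclusions.
   - Stop time: at least 2 weeks before sonidegib in item 8; at enrollment in exclusion 20 and item 19.

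6. **CK data near the trial dose.** The trial uses sonidegib 200 mg once daily. In Table 1 (single-agent study CLDE225X2101), patients at 100, 200 and 400 mg once daily number 5 + 6 + 4 = 15, with 0 Grade 3/4 CK dose-limiting events. The text beside the table adds that none appeared in later cycles below 800 mg once daily. With 0 of 15, the exact two-sided 95% upper limit is 1 − 0.025^(1/15) = 0.218, about 22%. The same text reports Grade 3/4 CK increases after cycle 1 in 2 patients at 250 mg twice daily (500 mg per day). None of these data are split by statin use.

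7. **Reach.** All 12 + 12 = 24 planned patients take sonidegib, so 24 is the ceiling on who could be exposed. The documents give no number of statin users, so no expected count follows.

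**The case against.** The best defence is that the protocol already has an on-treatment rule. Section 1.4.2 speaks of the period on sonidegib, and restarting a statin would defeat the purpose of exclusion 20. Section 4.2.3.2 and Table 17 concern buparlisib's CYP effects only, and a specific sonidegib warning can be read as prevailing over a general buparlisib list. Table 17 is also presented as a compiled database of substrates. It includes cyclosporine, sirolimus and everolimus, although exclusion 15 bars chronic immunosuppressive treatment, so a listing there does not override other rules.

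Much of this stands. A reader might infer that the protocol authorises these five statins. The documents do not support that: section 1.4.2 is part of the same protocol, and the result is a conflict, not a clear permission. The defence does not remove the conflict, because 4.2.3 permits whatever it does not except, and the investigator has to know of a background section to reach the safer answer.

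A reader might also infer that statins are the one drug exclusion left without an on-study rule, since 4.2.3.1 does restate others; for warfarin it says that therapeutic doses "or any other coumadin-derivative anticoagulants are not permitted". That contrast is not reliable. Exclusion 13 (colony-stimulating factors) has no counterpart in 4.2.3.1 or 4.2.3.2, and for exclusion 15 only the steroid half is limited there.

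The safeguards are real. Baseline CK above the upper limit of normal excludes a patient, CK is in the chemistry panel, Table 9 gives CK rules, and patients are asked to report new drugs. They detect or limit harm; they do not prevent the exposure.

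**Conclusion.** The conflict holds and should be corrected. Section 1.4.2 says to avoid statins apart from essential pravastatin, while the prescribing section names none as prohibited and leaves five others to discretion. Exclusion 20 does not close the gap for a statin started or restarted on treatment.

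The weight is modest. No Grade 3/4 CK elevation is reported below 800 mg once daily, and the trial dose is 200 mg. That reassurance is limited, because it rests on 15 patients in Table 1, on sonidegib alone, without regard to statin use. A reader might infer a quantified excess of muscle toxicity, or that all 24 patients are affected. Neither follows: only a patient given a statin on study is exposed, and the documents give neither that number nor a CK rate by statin use. No endpoint, sample size or analysis is touched.

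On pravastatin, the entry documents are ambiguous. Section 1.4.2 and item 8 could be read as a specific exception to exclusion 20 and item 19, but read literally the exclusions bar it. The documents do not settle which rule is intended.

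**What to change.** 1. Add a bullet to 4.2.3.1: statins, except pravastatin if the sponsor retains that exception, and other rhabdomyolysis-associated drugs (item 8 names clofibrate and gemfibrozil) are prohibited during sonidegib treatment.
2. Remove atorvastatin, simvastatin, lovastatin, fluvastatin and cerivastatin from Table 17, or footnote each as prohibited with a pointer to 4.2.3.1. This is right under either pravastatin rule, since none of the five is pravastatin.
3. Have the sponsor choose one pravastatin rule (no exception, or essential use with extra caution) and one stop time (at enrollment, or at least 2 weeks before the first dose). State both identically in 1.4.2, exclusion 20, 4.2.3.1 and Appendix B exclusion items 8 and 19.

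The cost is wording only. Steps 1 and 2 touch two places; step 3 touches four more (1.4.2, exclusion 20, items 8 and 19). No visits, tests or patients are added.
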